
4) Optune therapy should start within two weeks of start of adjuvant temozolomide, but not more than 7 weeks from the end of temozolomide/RT and will be continuous throughout study. Compliance documentation will be obtained every 4 weeks +/- 7 days.
							

5) Every 3 months until death. The only data required during survival follow-up is DOD.
							

6) Biochemistry panel will include electrolytes, creatinine, bilirubin, liver enzymes.
							

7) Patients will begin treatment with temozolomide at 4 weeks (+14 days) from end of radiotherapy. Cycle 1 will be dosed at 150mg/m² daily for 5 consecutive days of a 28-day cycle.
							

Study Procedure:	Screening ≤14 days prior to Day 0	Day 0 : Begin TMZ Treatment	Week 4 (-3/+7 days) and every 4 weeks until treatment stop	Week 8 (±7 days) and every 8 weeks only until treatment stop	Progression	After Treatment Stop (Week 4 (+/- 7 days) from end of treatment)	Survival follow-up

8) Patients will begin treatment with temozolomide Cycle 2 and subsequent cycles every 4 weeks (-3/+7 days) at 200mg/m² PO daily for 5 consecutive days, if CTC hematologic toxicity for cycle 1 is grade < 1 and the CTC non-hematologic toxicity for cycle 1 is grade ≤ 2. If dose escalation is not appropriate, the dose should remain at 150 mg/m² PO daily for 5 consecutive days for Cycle 2 and onward.
							

9) Verification of tissue availability and location should be determined at screening visit. When available, formalin fixed and paraffin embedded (FFPE), pathology slides and/or frozen samples will be obtained for primary tumors and first recurrent tumors.
							

10) Labs to be completed within 3 days for pre-TMZ cycles. Screening and other labs are within the visit windows noted. Pregnancy Test required for WOCBP only at Screening.
							

11) DICOM images will be shipped to Beth Israel Deaconess Medical Center for electric field mapping analysis at baseline, first progression and second progression. Imaging performed between shipping time points should be included in the next shipment.
							

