3 OBJECTIVES AND ENDPOINTS

TABLE 2: OBJECTIVES & ENDPOINTS

OBJECTIVES	ENDPOINTS	JUSTIFICATION FOR ENDPOINTS
Primary		
To determine whether TTFIELDS combined with adjuvant temozolomide increases OS in patients with newly diagnosed Grade II and III astrocytoma with TERT promoter mutation only compared to historical and contemporaneous controls.	OS measured in days from Study Day 0 until death. If the study ends and the participant is still living, OS will be measured in days from Study Day 0.	OS remains the primary concern within this patient population. Intent to Treat analysis will be used to determine if this objective is met.
Secondary		

 To determine whether the combination of TTFIELDS and adjuvant temozolomide is safe in the newly diagnosed high-risk Grade II and III astrocytoma. To determine whether TTFIELDS combined with adjuvant temozolomide increases PFS in patients with newly diagnosed Grade II and III astrocytoma with TERT promoter mutation only compared to historical and contemporaneous controls. To evaluate QOL using KPS, EORTC QLQ-C30/BN20, and MMSE in patients treated with TTFIELDS combined with adjuvant temozolomide compared to 	
 PFS measured in days from Day 0 to progression Safety measured by incidence and severity of Adverse Events and Toxicities. Quality of life measured by KPS, EORTC QLQ-C30/BN20, and MMSE Correlation between % Compliance with TTFIELDS and OS 	Safety, Efficacy, and Quality of Life measures for a more complete view of the effects of the study treatment(s).

historical and contemporaneous controls.		
Tertiary/Exploratory		

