9 CONTROL COHORT

This trial will include a control cohort that includes both historical and contemporaneous control patients. A minimum of 90 and a maximum of 100 patients will be enrolled in the control cohort. This is a non-interventional control group (data collection only). All patients in the control cohort will be enrolled at the same participating institutions. Risks associated with participation of the control cohort are minimal.

Historical controls will be gathered via chart review of patients completing chemo/RT after 1/1/2016 and before 5/20/2019; 5/20/2019 is the initial date of IRB approval for the coordinating center and first opened study site. Control patients completing chemo/RT after 5/20/2019 will be enrolled as contemporaneous controls.

Control subjects (contemporaneous or historical) will be enrolled via informed consent if consent is practicable. An IRB waiver of consent will be requested for historical control patients who may be deceased, no longer being followed or lost to follow-up.

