9.5 Control Cohort Limited Data Collection

Data collected for the historical and contemporaneous control group will be distinct from data collected for interventional patients in this study, as described below. Data for control patients is designed to be collected exclusively from chart review.

All control cohort documentation should be uploaded into the eCRF within 45 days of collection. Data extracted from the medical record shall be defined as collected on the day of extraction.

1. Informed Consent or waiver
2. Demographics

3. Pathology
4. Date of and extent of operation (GTR, partial, or biopsy)
5. Summary of Concurrent Chemo/RT

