6. KPS
7. Summary of Adjuvant Chemotherapy (TMZ dates, number of cycles)
8. Summary of Additional Therapies (therapy types, dates, number of cycles)
9. Date(s) of Progression
10. Date of Death (if applicable)
11. Tumor tissue samples (optional)

Tumor Tissue samples are optional for control cohort patients. Adverse Events are not collected, and not reportable for control patients. MRI Correlative Study does not include control cohort participants. Concomitant Medications will not be maintained for control patients, although applicable steroid doses may be recorded as part of the RANO form.

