10 STATISTICAL CONSIDERATIONS

10.1 Statistical Hypotheses

- Primary Efficacy Endpoint: overall survival (OS)

Control arm: the control arm will consist of both historical and contemporaneous control patients. Historical controls will consist of TERT mutation-only astrocytoma patients treated and followed by the participating sites between January 1, 2016 and May 20, 2019. As described above, these patients will have received standard treatment and would have met first tier inclusion/exclusion criteria for the study. Data for these patients will be collected via chart review. Contemporaneous controls will also consist of patients who qualify for the trial and receive standard treatment but decide not to proceed with the Optune experimental treatment because of personal preference. This personal preference must be non-medical in nature. Based on clinical experience, most commonly this non-medical patient personal preference preventing Optune use will be unwillingness to shave his/her head and/or unwillingness to wear a visible medical device on his/her head most of the day.

- N = 90 patients total in an expected mixture ranging between 80 historical controls and 10 contemporaneous controls to 60 historical controls and 30 contemporaneous controls.
- Assumed median survival = 22 months (based on Figure 3A in Eckel-Passow et al [12])
- Follow-up = up to 60 months for the historical controls, up to 60 months for the contemporaneous controls

Experimental treatment arm: TERT mutation-only astrocytoma patients who will receive standard treatment plus TFields therapy at one of 15 participating centers.

- N = 90 patients

- Assumed accrual rate = 2.5 patients/month accumulated over 15 centers
- Accrual period = 36 months
- Follow-up period after the end of accrual = 24 months
- Assumed survival time distribution = Weibull with accelerating hazard and proportional hazards

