10.2 Sample Size Determination

To assess sample size requirements for detecting an improvement in median overall survival (OS) in the experimental treatment arm relative to the historical control arm, we initially assumed 60 to 90 patients receiving standard treatment and follow-up between 1-2016 and 5-2019 would be available for chart review. We assumed that these historical control patients would have a maximum follow-up time of 60 months. For the experimental treatment, we assumed an accrual rate of 2.5 patients per month across 15 participating centers and an accrual period of 36 months, yielding an enrollment of 90 patients in the experimental arm. The patients in the experimental arm would be followed for an additional 24 months after the end of accrual. We considered improvements in median survival ranging from 4 to 8 months to be of clinical interest. We also assumed that survival times would follow a Weibull distribution with proportional hazards and an accelerating hazard function (shape parameter $k=2.0$, estimated from Figure 3A in Eckel-Passow et al [12]. We also considered a more slowly accelerating Weibull shape parameter of $k=1.8$. Under these assumptions, the power to detect **improvements** in median OS using a one-sided log-rank test (one-sided $\alpha=0.05$) are summarized in Table 10 for selected combinations of historical control sample size, Weibull shape parameter, and number of months improvement in median OS [detectable effect size methodology adapted from (Wu and Xiong, 2014)]. We then explored the effect of mixing historical and contemporaneous controls in select mixtures into a single control arm, noting a very slight improvement in power to detect improvements in survival. Overall, a control arm sample size of 90 patients, in historical/contemporaneous control mixtures of 90+0, 80+10, 70+20, and 60+30 all have at least 80% power to detect improvements in survival between 6 and 8 months.

TABLE 10: POWER TO DETECT M MONTHS IMPROVEMENT IN MEDIAN OVERALL SURVIVAL UNDER SELECTED SCENARIOS

Accrual rate (N/mo)	Accrual period (mos)	Follow-up period (mos)	Trial N	Hx Ctl+ Contemp N	Weibull shape k	Power to detect M months improvement in median OS at one-sided $\alpha=0.05$ using the log-rank test				
						M = 4	5	6	7	8
2.5	36	24	90	50+ 0	2.0	0.525	0.667	0.782	0.866	0.922
2.5	36	24	90	60+ 0	2.0	0.565	0.711	0.823	0.899	0.946
2.5	36	24	90	70+ 0	2.0	0.598	0.745	0.853	0.922	0.962
2.5	36	24	90	80+ 0	2.0	0.626	0.773	0.876	0.938	0.972

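### Control-arm overall survival is taken from charts with a death date but no vital status or date last known alive, and no rule covers unknown status, so controls have no sound censoring time

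*Combined protocol and SAP*

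**What the plan says.** **Controls.** Section 9.5 states: "Data for control patients is designed to be collected exclusively from chart review". Of its eleven items, the only one on survival is item 10, "Date of Death (if applicable"). Neither that list nor the control enrolment list in section 11.2.2.1 asks for vital status, last contact or date last known alive. The dates that are listed belong to surgery, temozolomide, additional therapies and progression. Section 9 foresees patients whose outcome is unknown: "An IRB waiver of consent will be requested for historical control patients who may be deceased, no longer being followed or lost to follow-up". Section 10.1 expects 60 to 80 of the 90 controls to be historical.

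**TTFields arm.** Footnote 5 of the Schedule of Activities reads: "Every 3 months until death. The only data required during survival follow-up is DOD". Sections 6.1.1.3.2.6, 6.1.2.6 and 8.2.2 repeat the 3-monthly contact. Section 7.3 adds tracing by telephone and letter, and contact with the legally authorized representative. That tracing starts from a missed study visit, and controls have none.

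**Endpoint rule.** Beyond death, Table 2 (section 3) says only: "If the study ends and the participant is still living, OS will be measured in days from Study Day 0". Section 10.2.1 names the log-rank test without a censoring rule. Section 11.1.9.2 lists loss to follow-up among the ways survival follow-up ends, but attaches no censoring date to it.

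**The concern.** A survival comparison needs each patient's death date, or the last date on which the patient was known to be alive. The plan secures this in one arm and leaves it open in the other. A control who moved to hospice, home care or another hospital may have died without the chart showing it. On the listed items that patient looks the same as a control who is alive and well.

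Someone must then choose a censoring date for every control with a blank death field. The plan does not make that choice, so it could be made after outcomes are known. Every date that the list offers has a fault. Data cut-off or the extraction day credits patients with survival that nobody observed. The last therapy or progression date cuts true survivors short. The first can hide a real benefit; the second can produce an apparent one.

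**Working it through.** **Inputs from the plan (sections 10.1, 10.2, Table 10).** "Assumed median survival = 22 months" for controls; Weibull shape k = 2.0; 90 versus 90; one-sided log-rank test at 0.05; treatment accrual 36 months plus 24 months of follow-up; controls followed for up to 60 months. On effect size: "We considered improvements in median survival ranging from 4 to 8 months to be of clinical interest".

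**Assumptions, not in the plan.** The fraction p of control deaths missing from the chart; the spread of control follow-up (uniform over 24 to 60 months, or 60 months for all); and the timing of the last dated chart item (30 to 80% of observed time).

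**Step 1: the plan's own figure.** For a 6-month gain, HR = (22/28)² = 0.617. With follow-up uniform over 24 to 60 months in both arms, expected deaths are 78.4 (controls) + 67.6 (TTFields) = 146.0. Power = Φ(√(146.0 × 0.25) × |ln 0.617| − 1.645) = Φ(2.914 − 1.645) = 0.898. Table 10 gives 0.894, so it reproduces. It allows for no missed deaths.

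**Step 2: controls with missed deaths carried alive to cut-off.** The apparent control median solves (1 − p)S(t) + p = 0.5, with S(t) = exp(−ln 2 × (t/22)²). For p = 10%, S = 0.40/0.90 = 0.444 and t = 22 × √(ln 2.25/ln 2) = 23.8 months. For 5% and 20% it is 22.8 and 26.2 months.

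Simulated log-rank power for a true 6-month gain (4,000 trials per cell):

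| Missed | Controls 24–60 months | Controls all 60 months |
|---|---|---|
| 0% | 0.90 (HR 0.61) | 0.91 |
| 5% | 0.62 (HR 0.71) | 0.61 |
| 10% | 0.31 (HR 0.82) | 0.25 |

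With no true effect and the 24–60 month spread, false positives fall to 0.8% at 5% missed and 0.1% at 10%. This rule hides benefit; it does not create it.

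**Step 3: every control without a death date censored at the last therapy or progression date, no true effect.**
- *Follow-up 24 to 60 months.* About 90 − 78.4 = 11.6 controls are alive at cut-off and lose survival time they really had. HR is about 0.84 to 0.87. One-sided false positives are about 30% with no deaths missed and about 20% with 10% missed.
- *All controls at 60 months.* S(60) = exp(−0.693 × (60/22)²) = 0.006, about 0.5 of 90 patients, so almost nobody is cut short. HR is 0.99 to 1.03 and false positives are 6% to 3.5%.

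**Step 4: censoring at a true date last known alive, 6-month gain.**
- *Loss unrelated to prognosis.* HR stays at about 0.61; power is 0.88 at 10% lost and 0.86 at 30%.
- *Loss shortly before death, 10% of control deaths.* Power is 0.74 (contact ends 3 months before death, 24–60 month spread) or 0.77 (contact ends within 6 months of death, all at 60 months). A correct rule removes most of the damage, not all of it.

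**The case against.** A reader might infer that controls who left the site are counted as survivors, and that the primary comparison is therefore biased against TTFields. The documents do not say so. Table 2 speaks of participants still living, not of those whose status is unknown, and no section carries a lost control forward as alive. Nor is the extraction day the only other date available: surgery, therapy and progression dates each show that the patient was alive then. As Step 3 shows, using those dates can push the bias the other way. Neither its direction nor its existence is fixed by the text.

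The contrast between arms also has limits. Section 7.3 provides for loss in the TTFields arm too. Section 10.1 describes historical controls as treated and followed at the participating sites, and charts may record deaths elsewhere. Section 11.1.8 has missing data queried. The actual case report form fields are not in the documents.

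These points remove the claim of a known bias in a known direction. They do not supply a censoring date. The listed dates are event dates rather than contact dates, nothing tells the analyst to use them, and a query cannot resolve a blank that is valid whenever death is not applicable.

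**Conclusion.** The gap is real and should be fixed. The primary endpoint is followed actively in one arm and from charts in the other, and the items listed for controls cannot give a sound censoring time. Carrying controls with missed deaths alive to cut-off cuts 6-month power from about 0.90 to about 0.6 at 5% missed and 0.25 to 0.31 at 10%; ten percent of 90 controls is nine charts. Censoring at the last therapy or progression date can instead raise one-sided false positives from 5% to about 20 to 30%, but only when many controls are alive at a cut-off well short of 60 months.

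The sizes are conditional: the documents give no missed-death rate, no distribution of control follow-up and no timing for the last dated item. Table 10 itself is not in error. What is established is an undefined rule and a missing data item for the primary endpoint, not a bias of known size or sign.

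**What to change.** 1. In section 9.5, replace item 10 with: *Vital status, date of death or date last known alive, and source.*
2. In Table 2, state that patients in either arm not known to be dead are censored at the date last known alive, and never at study end, extraction date, or last treatment or progression date.
3. For every control without a death date, repeat the chart review of vital status once at the common data cut-off. Use telephone contact only where the control consented to it: section 9 defines this cohort as data collection only, and neither control list records a legally authorized representative.
4. Add a sensitivity analysis for controls with unknown status, because loss close to death stays informative even under the correct rule (power about 0.74 to 0.77 at 10%).

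**Cost.** One extra chart field and one repeat review for 90 to 100 controls, and earlier censoring for some. Ascertainment will remain less complete for controls under a consent waiver, and the report should say so. The change is best made before the data are locked and coded (section 11.1.9.2), when tracing becomes harder.

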10 STATISTICAL CONSIDERATIONS

10.1 Statistical Hypotheses

- Primary Efficacy Endpoint: overall survival (OS)

Control arm: the control arm will consist of both historical and contemporaneous control patients. Historical controls will consist of TERT mutation-only astrocytoma patients treated and followed by the participating sites between January 1, 2016 and May 20, 2019. As described above, these patients will have received standard treatment and would have met first tier inclusion/exclusion criteria for the study. Data for these patients will be collected via chart review. Contemporaneous controls will also consist of patients who qualify for the trial and receive standard treatment but decide not to proceed with the Optune experimental treatment because of personal preference. This personal preference must be non-medical in nature. Based on clinical experience, most commonly this non-medical patient personal preference preventing Optune use will be unwillingness to shave his/her head and/or unwillingness to wear a visible medical device on his/her head most of the day.

- N = 90 patients total in an expected mixture ranging between 80 historical controls and 10 contemporaneous controls to 60 historical controls and 30 contemporaneous controls.
- Assumed median survival = 22 months (based on Figure 3A in Eckel-Passow et al [12])
- Follow-up = up to 60 months for the historical controls, up to 60 months for the contemporaneous controls

Experimental treatment arm: TERT mutation-only astrocytoma patients who will receive standard treatment plus TFields therapy at one of 15 participating centers.

- N = 90 patients

- Assumed accrual rate = 2.5 patients/month accumulated over 15 centers
- Accrual period = 36 months
- Follow-up period after the end of accrual = 24 months
- Assumed survival time distribution = Weibull with accelerating hazard and proportional hazards

10.2 Sample Size Determination

To assess sample size requirements for detecting an improvement in median overall survival (OS) in the experimental treatment arm relative to the historical control arm, we initially assumed 60 to 90 patients receiving standard treatment and follow-up between 1-2016 and 5-2019 would be available for chart review. We assumed that these historical control patients would have a maximum follow-up time of 60 months. For the experimental treatment, we assumed an accrual rate of 2.5 patients per month across 15 participating centers and an accrual period of 36 months, yielding an enrollment of 90 patients in the experimental arm. The patients in the experimental arm would be followed for an additional 24 months after the end of accrual. We considered improvements in median survival ranging from 4 to 8 months to be of clinical interest. We also assumed that survival times would follow a Weibull distribution with proportional hazards and an accelerating hazard function (shape parameter $k=2.0$, estimated from Figure 3A in Eckel-Passow et al [12]. We also considered a more slowly accelerating Weibull shape parameter of $k=1.8$. Under these assumptions, the power to detect **improvements** in median OS using a one-sided log-rank test (one-sided $\alpha=0.05$) are summarized in Table 10 for selected combinations of historical control sample size, Weibull shape parameter, and number of months improvement in median OS [detectable effect size methodology adapted from (Wu and Xiong, 2014)]. We then explored the effect of mixing historical and contemporaneous controls in select mixtures into a single control arm, noting a very slight improvement in power to detect improvements in survival. Overall, a control arm sample size of 90 patients, in historical/contemporaneous control mixtures of 90+0, 80+10, 70+20, and 60+30 all have at least 80% power to detect improvements in survival between 6 and 8 months.

TABLE 10: POWER TO DETECT M MONTHS IMPROVEMENT IN MEDIAN OVERALL SURVIVAL UNDER SELECTED SCENARIOS

Accrual rate (N/mo)	Accrual period (mos)	Follow-up period (mos)	Trial N	Hx Ctl+ Contemp N	Weibull shape k	Power to detect M months improvement in median OS at one-sided $\alpha=0.05$ using the log-rank test				
						M = 4	5	6	7	8
2.5	36	24	90	50+ 0	2.0	0.525	0.667	0.782	0.866	0.922
2.5	36	24	90	60+ 0	2.0	0.565	0.711	0.823	0.899	0.946
2.5	36	24	90	70+ 0	2.0	0.598	0.745	0.853	0.922	0.962
2.5	36	24	90	80+ 0	2.0	0.626	0.773	0.876	0.938	0.972
2.5	36	24	90	90+ 0	2.0	0.649	0.796	0.894	0.950	0.979

2.8	36	24	90	80+10	2.0	0.650	0.796	0.894	0.950	0.979
3.1	36	24	90	70+20	2.0	0.651	0.797	0.895	0.951	0.979

3.3	36	24	90	60+30	2.0	0.652	0.798	0.895	0.951	0.979
=====										
2.5	36	24	90	50	1.8	0.447	0.577	0.692	0.787	0.858
2.5	36	24	90	60	1.8	0.483	0.620	0.737	0.828	0.892
2.5	36	24	90	70	1.8	0.513	0.654	0.771	0.858	0.916
2.5	36	24	90	80	1.8	0.538	0.683	0.798	0.880	0.933
2.5	36	24	90	90	1.8	0.560	0.707	0.820	0.898	0.946
2.5	36	24	90	100	1.8	0.579	0.727	0.838	0.912	0.955

2.8	36	24	90	80+10	1.8	0.561	0.708	0.821	0.899	0.946
3.1	36	24	90	70+20	1.8	0.562	0.709	0.822	0.899	0.947
3.3	36	24	90	60+30	1.8	0.563	0.710	0.823	0.900	0.947

